## **12 SUBJECT TREATMENT AND STUDY PROCEDURES**

### **12.1 Pre-screening**

During the pre-screening phase, the investigator or designee performs an initial evaluation of potential candidates for study eligibility. This initial pre-screening phase may include review of existing patient information (e.g., CT scans, previously performed diagnostic measures, laboratory studies, medical history, physical examination).

### **12.2 Informed Consent, Enrollment and Screening**

If the patient appears to be a potential candidate for the study based on existing information, written informed consent will be obtained. No protocol required testing will be performed solely for the purposes of this study prior to obtaining written informed consent.

Clinical investigators or designees will approach the patient to obtain written informed consent. The background of the proposed study, the dilation procedure, implantation, the follow-up schedule and all potential risks and benefits will be carefully explained to each patient. The clinical investigator or designee obtaining the informed consent shall be in compliance with ICF regulations:

Each patient must sign and date the ICF approved by an appropriate Institutional Review Board (IRB). Patients are considered enrolled in the study upon signing the IRB-approved ICF. Enrolled

subjects will be assigned unique identifying codes by the Electronic Data Capture (EDC) system and entered into the study database. Upon enrollment, subjects will have a screening assessment.

The screening assessment will include:

- Review of CT scan (must be performed  $\leq$  90 days prior to baseline procedure; see Section 13)
- Endoscopic evaluation with grading and video recording; and
- Female subjects of childbearing potential must confirm their nursing status, undergo pregnancy test to confirm they are not pregnant.

If the screening visit occurs on the same day as the baseline/procedure visit, all assessments will be recorded in the baseline visit forms (see Section 7). All subjects who do not pass the screening assessment, including successfully completed in-office bilateral balloon dilation of the FSO with no complication and amenable for PROPEL Contour placement will be considered as screen failures and will be terminated from the study. The reason for ineligibility will be recorded in the EDC system.

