Device malfunction	
For an investigational medical device: Failure to perform in accordance with its intended purpose when used in accordance with the instructions for use or clinical investigation plan (CIP), or Investigators' Brochure (IB). [ISO 14155:2020]
 
Failure to meet its performance specifications or otherwise perform as intended. The intended performance of a device refers to the intended use for which the device is labeled or marketed. [21 CFR 803]

Enrolled	Subjects are considered enrolled upon signing the IRB-approved informed consent form.
Frontal sinus ostia/ostium (FSO)	Refers to the natural frontal sinus openings
Frontal sinus outflow tract (FSOT)	Refers to the region of the frontal sinus surrounding the FSO, bordered superiorly by the frontal infundibulum and inferiorly by the frontal recess
Implant delivery success	Successful access and deployment of the PROPEL Contour Sinus Implant into the FSO. Delivery is considered successful if the procedure concludes with correct implant placement on the intended side, even if a second attempt to place the implant is necessary. An attempted deployment

	
occurs when the investigator introduces the delivery system into the subject's nostril with the intent of placing an implant.
 
The proportion of successful deployments is defined as a fraction where the numerator is the number of successful deployments and the denominator is the number of sinuses in which a deployment was attempted.

Inflammation score	For the purpose of the endoscopic scoring method in this study, the term inflammation is a global descriptor that includes erythema, edema and/or polypoid changes. The inflammation present in the frontal recess/FSO is estimated visually based on the endoscopic examination on a scale ranging from 0 (no visible inflammation) to 100 (severe inflammation) involving extensive erythema, or polyposis
Institutional Review Board (IRB)	An independent body whose responsibility it is to review clinical investigations in order to protect the rights, safety and well-being of human subjects participating in a clinical investigation. The primary purpose of such review is to assure the protection of the rights, safety, and welfare of human subjects. The IRB should be established, operated, and function in conformance with 21 CFR 56.

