### **9.4 Safety Measures**

All adverse events (AEs) for each subject from the time the subject gives informed consent through Day 180 will be recorded in the electronic data capture (EDC) system and monitored. Each AE will be evaluated by the clinical investigators for their seriousness and relationship to the study devices. Where possible and if applicable, AEs will be localized to a sinus location.

Safety will be determined by assessment of, adverse device effects (ADE), serious adverse events (SAEs), unanticipated adverse device effect (UADE) and unanticipated serious adverse device effect (USADE) from enrollment through Day 180 post-procedure (Section 4). All events will be separated between those attributed to PROPEL Contour Sinus Implant, those attributed to Cube Navigation System, VenSure™ Nav Balloon Device, Inflation device, Balloon Dilatation Procedure, Implant Placement Procedure, and those that are a mix or indistinguishable.

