#### General inclusion criteria

- a. Patient has provided written informed consent using a form approved by the reviewing IRB.
- b. Patient is 18 years of age or older.
- c. Patient is willing and able to comply with protocol requirements.
- d. Patient has confirmed diagnosis of CRS per International Consensus Statement on Allergy and Rhinology: Rhinosinusitis 2021 (ICAR:RS) guidelines.

Patient must have  $\geq$  12 weeks of:

Two or more of the following symptoms:

- nasal obstruction or congestion
- nasal discharge (rhinorrhea or post-nasal drip)
- facial pain/pressure
- reduction/loss of smell

And one or more of the following findings:

- Evidence of inflammation on paranasal sinus examination or CT

- Evidence of purulence coming from paranasal sinuses or ostiomeatal complex
- e. In the opinion of the investigator, treatment with the PROPEL Contour Sinus Implant as an adjunct to frontal BSD with a 6 mm balloon is technically feasible and clinically indicated in both FSO.
- f. Female patients of reproductive age and potential must not be pregnant or nursing, and patient agrees to avoid becoming pregnant during their participation in the study.

*CT Imaging inclusion criteria*

- g. Patient has bilateral disease in the frontal sinus (Lund-Mackay score  $\geq 1$  on each side) on CT scan performed  $\leq 90$  days prior to the baseline procedure.

*Intraprocedural inclusion criteria*

- h. Patient is able to tolerate topical/local anesthesia.
- i. Confirmation of bilateral FSO access with navigation assistance
- j. A successfully completed in-office bilateral balloon dilation of the FSO with no complication on either side that, in the opinion of the investigator is amenable for PROPEL Contour Sinus Implant placement in both FSO.

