## **12.4 Follow-Up**

The follow-up period begins immediately post-treatment (once the study implant is placed in the subject in the clinical investigator's office).

At each follow-up visit, the subject will undergo endoscopic evaluation with grading and video recording at Day 21, 45, 90 and 180 (end of study). After suctioning, endoscopic grading is performed and recorded on the endoscopic assessment CRFs. Suctioning and clearing mucous/stent debris of the FSO should be completed prior to Day 45 CT scan. It is preferred that the PROPEL Contour Sinus Implant be left in place for 30 days but can be removed at investigator discretion.

An overview of the assessments to be performed at each follow-up interval along with required timing is provided in Section 7.

A CT scan is repeated at Day 45 (primary endpoint) and again at Day 180. The acquisition and measurements by the centralized imaging core lab are detailed in Section 13.

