## 16 ASSESSMENT OF SAFETY

### 16.1 Specification of Safety Parameters

Adverse events (AE) for each subject from the time the subject gives written informed consent (enrollment) through Day 180 (end of study) will be recorded in the EDC system and monitored. Each AE will be evaluated by clinical investigators in terms of severity (i.e., mild, moderate, severe) as well as strength of relationship (i.e., not related, unlikely related, probably related, definitely related, indeterminate) to the study drug (mometasone furoate), study devices, and procedures (BSD, implant placement). Each AE will be reviewed by sponsor in accordance with sponsor's SOP. The study sponsor is responsible for ensuring that all AEs are appropriately recorded, adjudicated and, when applicable, reported to the government(s), ethics committee(s) and other study centers per applicable regulations.

Subjects with CRS experience a persisting set of symptoms associated with the disease and may continue to present with a wide range of symptoms during the recovery process after in-office balloon dilation. These may include symptoms such as pain and discomfort, headache, decreased sense of smell, crusting, epistaxis, and other symptoms. Patients healing appropriately after in-office procedure may suffer from acute infections and/or inflammatory exacerbations unrelated to the procedure due to the natural course of their CRS. Therefore, clinical investigators will evaluate the occurrence of AEs excluding usual post-operative recovery signs and symptoms experienced by study subjects, unless corroborated by objective findings and/or requiring specific medical or therapeutic interventions (e.g., antibiotics, repeat ESS).

Note: The need for medical or surgical intervention in the FSO post-dilation that is captured on the endoscopic assessment CRF will not be considered as an AE. Likewise, other endoscopic findings such as inflammation, adhesion/scarring, and edema of the FSO will not be considered as AEs.

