### 16.4 Guidelines for AE Reporting

All AEs, regardless of seriousness or relationship to the study devices, will be recorded in the EDC system and will include event description, date of onset, investigator's assessment of severity, relationship to study devices, and date of resolution/stabilization of the event. All AEs occurring while on study must be documented appropriately regardless of relationship. All AEs will be followed through end of the study.

Any pre-existing medical condition that is present at the time of screening will not be reported as an AE. The occurrence of diagnostic or elective surgical procedures for a pre-existing condition will not be recorded as an AE, unless the condition becomes more severe or results in an AE.

Whenever possible, diagnosis or single syndrome should be reported instead of symptoms. The investigator should specify the date of onset, severity, action taken with respect to the study device(s), corrective treatment/therapy given, additional investigations performed, outcome, and his/her opinion as to whether there is a reasonable possibility that the AE was caused by the study device(s).

The investigator should take appropriate measures to follow all AEs until resolution or until progression has been stabilized, or until study exit, to ensure the safety of the subjects. If the AE continues beyond the last planned visit per protocol and/or the subject withdraws from the study, clinical investigators should follow the subjects according to standard of care.

If a subject decides to withdraw from the study, clinical investigator should follow patients with ongoing AEs till resolution according to the standard of care.

An investigator will submit to the sponsor a report of AEs occurring during this investigation as defined in the table below.

Type of Report	Submission Schedule
Device-related AE	Verbal report or initial entry into the AE CRF within 24 hours from assessment followed by written report within 10 working days
Subject Death	Verbal report within 24 hours followed by a written report within 2 working days
SAE/SADE/UADE/US ADE	Verbal report within 24 hours followed by a written report within 5 working days

The investigator will report the above to the reviewing IRB per the IRB's guidelines. The study sponsor will be responsible for reporting safety events to the Food and Drug Administration (FDA) as required per 21 CFR 812 and 21 CFR 803.

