## 17.1 Potential Risks

Risks associated with balloon dilation of the sinuses, as well as the placement and use of the PROPEL Contour Sinus Implant in the FSO are anticipated to be similar to those experienced by subjects who undergo balloon dilation of the sinuses as well as placement of other sinus stents.

Consequently, the risks potentially associated with the use of the sinus balloons may include but are not limited to the following:

- Epistaxis
- Cerebrospinal fluid leak
- Pneumocephalus
- Damage of the orbital wall or other ocular structures
- Impaired or loss of vision
- Impaired tearing
- Periorbital cellulitis/edema
- Infection
- Facial/nasal pain
- Facial/nasal discomfort
- Headache

Accordingly, the risks potentially associated with the placement of the PROPEL Contour Sinus Implant are:

- Special care should be taken to avoid bending, twisting or damaging the implant.
- The implant is not designed to be modified by the physician.
- The implant is not intended to be compressed and loaded into the delivery system more than two times.
- The implant must be placed under endoscopic visualization.
- The implant exhibits no antimicrobial properties.
- Foreign body reaction may occur as is possible with most surgical adjuncts.
- In rare instances, the physiochemical condition associated with sinus surgery, both with and without sinus implants or packing, may present a risk of toxic shock syndrome (TSS).
- Pediatric Use: The safety and effectiveness of the implant in pediatric patients have not been established.

- Pregnancy and Nursing Females: The safety and effectiveness of the implant in pregnant or nursing females have not been established.

Risks or side effects associated with the intranasal use of intranasal mometasone furoate (study drug):

- Nasal irritation
- Hypersensitivity reaction
- Intranasal bleeding
- Localized infection (bacterial, fungal colonization or viral) in the nose or pharynx
- Nasal burning
- Nasal dryness
- Susceptibility to secondary infections due to bacteria, fungi or viruses
- Glaucoma or elevation of intraocular pressure
- Cataracts or change in lens opacities
- Headache
- Pharyngitis

General side effects associated with steroids:

- Alteration of the HPA axis including growth suppression
- Immunosuppression
- Hypersensitivity reactions
- Headache
- Epistaxis
- Coughing
- Vomiting
- Candidiasis
- Glaucoma/elevation in intraocular pressure
- Cataracts or change in lens opacities
- Arthralgia
- Myalgia

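### Subjects dilated with the study balloon but not randomised are terminated as screen failures, so no scheduled contact exists to carry out the rule that adverse events are recorded through Day 180

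*Protocol*

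**What the plan says.** **Eligibility and termination.** Protocol 12.3.1 has the frontal dilation done with the study balloon and navigation system, and final eligibility confirmed afterwards. Inclusion criterion j (11.1) requires "A successfully completed in-office bilateral balloon dilation of the FSO with no complication on either side" and an opening that the investigator considers suitable for the implant on both sides. Under 12.2, subjects who do not meet this "with no complication and amenable for PROPEL Contour placement will be considered as screen failures and will be terminated from the study".

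**Follow-up.** Protocol 12.4: "The follow-up period begins immediately post-treatment (once the study implant is placed in the subject". The schedule in Section 7 has visits at Day 21, 45, 90 and 180 and no separate contact for a subject who was dilated but not implanted.

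**Adverse event recording.** Section 4: "Subjects are considered enrolled upon signing the IRB-approved informed consent form". Section 9.4: "All adverse events (AEs) for each subject from the time the subject gives informed consent through Day 180 will be recorded". Section 16.1 says the same: events are recorded "from the time the subject gives written informed consent (enrollment) through Day 180 (end of study) will be recorded in the EDC system". Section 9.4 also separates events by implant, navigation system, balloon, inflation device, dilation procedure and placement procedure.

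**Safety tables.** Protocol 18.6 and SAP 4.5 define the safety population as those exposed to the implant. SAP 9.7 presents all safety summaries on that population and lists every adverse event. Enrolled subjects without implant exposure get a separate summary (18.6, SAP 4.5), and SAP 7 reports screen failures in a listing and a table.

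**The concern.** Criterion j can be judged only once a study device has been used. The subjects it removes have been exposed to the balloon, and some are removed because the dilation was complicated or incomplete. They are enrolled, so the consent-to-Day-180 rule applies to them, but the plan gives the site no occasion on which to apply it.

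On balloon risk, Section 17.1 says that "the risks potentially associated with the use of the sinus balloons may include but are not limited to the following", and its list includes infection, periorbital cellulitis or edema, and cerebrospinal fluid leak. The documents do not say when these appear. It is my clinical assumption that some need not be evident before the subject leaves the procedure visit. If so, a later event in such a subject reaches the study only if someone volunteers it.

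A lesser issue concerns the tables. If criterion j is followed, any subject terminated for a complication recognised before randomisation is outside the implant-exposed tables by rule. The dilation-attributed counts in those tables then describe only subjects whose dilation was judged free of complication at the time.

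**Working it through.** **1. The rules side by side.** The plan has no figure to reproduce on this point, so the check starts with the text.

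| Rule | Implanted subject | Dilated, fails criterion j |
|---|---|---|
| Enrolled at consent (4) | Yes | Yes |
| Exposed to study balloon (12.3.1) | Yes | Yes |
| Events recorded through Day 180 (9.4, 16.1) | Yes | Yes, as written |
| Follow-up period starts (12.4) | Yes | No |
| Scheduled contacts after the procedure visit (7) | 4 | 0 |
| In the main safety tables (18.6, SAP 4.5, 9.7) | Yes | No; separate summary |

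The third and fifth rows do not fit together in the last column.

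**2. What is already covered.** An event seen at the procedure visit falls within the recording period, is reportable under 16.4, and appears in the listings and the separate summary. For an event still open, 16.4 says: "If the AE continues beyond the last planned visit per protocol and/or the subject withdraws from the study", the investigator should follow the subject by standard of care. That arguably reaches a terminated subject, although it does not name one. Section 16.4 also lets study follow-up of an event end at study exit. What remains uncovered is a new event after termination, or the study's record of how an open one evolves.

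**3. How many subjects.** The documents give no rate for failing criterion j. Let f be the assumed share of dilated subjects who fail. To reach 80 randomised, the number dilated is 80/(1 − f), and the number terminated is n = 80/(1 − f) − 80:

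- f = 2%: 81.6 dilated, 1.6 terminated; take 2 of 82
- f = 5%: 84.2 and 4.2; take 4 of 84
- f = 10%: 88.9 and 8.9; take 9 of 89
- f = 20%: 100.0 and 20.0; take 20 of 100

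**4. How many late events.** Let d be the assumed chance that a terminated subject has a new delayed event. The expected number is n × d, and the chance of at least one is 1 − (1 − d)^n:

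| n | d = 1% | d = 5% | d = 10% |
|---|---|---|---|
| 2 | 0.02; 2.0% | 0.10; 9.8% | 0.20; 19.0% |
| 4 | 0.04; 3.9% | 0.20; 18.5% | 0.40; 34.4% |
| 9 | 0.09; 8.6% | 0.45; 37.0% | 0.90; 61.3% |
| 20 | 0.20; 18.2% | 1.00; 64.2% | 2.00; 87.8% |

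Both f and d are assumptions and no cell is better supported than another. The table shows only that the answer could lie almost anywhere between negligible and likely.

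**5. Effect on a table.** One complication recognised before randomisation counts for nothing in the implant-exposed tables. Over all dilated subjects it would count for 1/82 = 1.2% down to 1/100 = 1.0%.

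**The case against.** The strongest reply is that the plan already handles most of this. The recording rule covers each subject, and 12.2 does not say that recording stops at termination, so an event that becomes known is still recordable. Open events have standard-of-care follow-up. These subjects were clinical candidates for dilation, so the lack of a study visit is not a lack of care. This stands, and it narrows the point to scheduled detection of new or evolving events. It does not supply a contact at which they would be asked about.

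On the tables, the reply is stronger. The objective is implant efficacy, no dilation complication rate is an endpoint, unexposed subjects are summarised separately, and all events are listed. An implant-based safety population is a legitimate choice. The table mock-ups and flow diagram are not visible in the supplied text and may specify what the separate summary contains. The table request is therefore secondary.

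Three stronger readings are tempting, and the documents support none of them:

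- **That dilation harms in these subjects are lost.** Those seen at the procedure visit are recorded and reported.
- **That the number terminated measures the number harmed.** Criterion j also fails subjects whose opening is merely unsuitable for the implant.
- **That the main tables contain no dilation harm.** Events that emerge later in implanted subjects do enter them, as may a minor early event that the investigator did not judge to be a complication.

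**Conclusion.** The point holds in a limited form and is worth fixing. Following 12.2 and 12.4 as written leaves enrolled, balloon-exposed subjects with no scheduled contact at which the consent-to-Day-180 rule in 9.4 and 16.1 could be met. The gap is limited to balloon, navigation or dilation harms that are new or evolve after the procedure visit.

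Its size cannot be determined from the documents. The range of about 2 to 20 subjects rests wholly on an assumed failure rate of 2% to 20%, and any count of missed events needs a second assumed rate. The primary and key secondary efficacy analyses are untouched. This improves safety capture in a post-market study that the sponsor treats as non-significant risk (19.14); it does not threaten the result.

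**What to change.** **Main change, in 12.2 and 12.4.** Keep immediate termination for subjects in whom no study balloon was introduced. For those dilated but not randomised, require:

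- one remote contact for adverse events and device deficiencies in the Day 21 window (21 ± 7, so Day 14 to 28);
- follow-up of any open event to resolution or stabilisation.

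Section 21.1 already accepts virtual collection of both items; make it a standing rule outside the COVID-19 section. No CT, endoscopy or questionnaire is needed. Leave 9.4 and 16.1 as they are, so that any event that becomes known by Day 180 is still recorded. Writing the shorter window into those sections would reduce the stated capture.

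**Secondary change, in 18.6 and SAP 4.5 and 9.7.** Keep the implant-exposed tables and the separate summary. Add one table of events attributed to the balloon, navigation system, inflation device or dilation procedure, over all subjects in whom dilation was attempted.

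**Cost.** Some wording, one extra denominator, and about 2 to 20 remote contacts over the assumed range. Against 80 × 4 = 320 planned follow-up visits, that is 2/320 = 0.6% to 20/320 = 6.3%. The reported dilation event rate may look slightly less favourable. New events after the single contact would remain unscheduled, which is proportionate here.
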